3.2. Measures by Construct and Time point

Tables 1 and 2 describe the study measures by construct.

Table 1: Measures used in the study, organized by construct and method.

Measures and Constructs	Time point
Moderators	
Gender, age, race, household composition, school, truancy, support, goals, interest in discussing health risks with provider	T1(A)
Number of visits with provider	T2(A)
Health Self-Efficacy	T1(A), T2 (A), T3(A), T4(A), T5(A)
Caregiver Concerns	
Guidelines for Adolescent Preventative Services Caregiver Questionnaire: adolescent health risk behavior concerns.	T1(C)
Perception of provider engagement with the caregiver	T2 (C)
Intermediary Targets	
Health Motivation (Readiness to Change Rulers): Self-report used to assess adolescent motivation for change among specific health behaviors.	T1(A), T2 (A), T3(A), T4(A), T5(A)
Adolescent Report of the Visit: adolescent-report of the PCPs' delivery of risk behavior screening and counseling based on risk level.	T2 (A)
Interval Receipt of Care: adolescent self-report of extent of follow up care.	T3 (A), T4(A), T5(A)
Main Outcomes: Satisfaction & Perception of PCP Communication	

Satisfaction Questionnaire: self-report of satisfaction with care based on items adapted from the Consumer Assessment of Healthcare Providers and Systems (CAHPS) measure.	T2(A/C)
Adolescent Perception of Patient-Centeredness: adolescent self-report of how adolescents feel about visits with their primary caregiver.	T2(A)
Main Outcomes: Health Risk Dimensions*	
Alcohol Consumption and Marijuana Use: self-report based on items about typical quantity and frequency of drinking, smoking/using tobacco, and marijuana use (each calculated separately) over the past 30 days.	T1(A), T3(A), T4(A), T5(A)
Fruit and Vegetable Screener: self-report of fruit and vegetable consumption.	T1(A), T3(A), T4(A), T5(A)
Physical Activity Screener: self-report of physical activity.	T1(A), T3 (A), T4(A),T5(A)
Sexual Risk: self-report of sexual activity, birth control, and condom use.	T1(A), T3(A), T4(A), T5(A)
Patient Health Questionnaire-9 (PHQ-9): self-report of DSM-V symptoms for depression.	T1(A), T3(A), T4(A), T5(A)
Safety: self-report to assess behaviors that contribute to unintentional injuries (e.g., seat belt use, helmet use).	T1(A), T3(A), T4(A), T5(A)

Key: T1 = Timepoint 1 (Baseline) T4 = Timepoint 4 (6 month)
T2 = Timepoint 2 (1-day) T5 = Timepoint 5 (1 year)
T3 = Timepoint 3 (3-month)
A = Adolescent survey

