C = Caregiver survey *See Table 2 for Individual Health Risk Outcomes and Summary Risk Variable

Table 2: Summary Risk Variable and Individual Health Risk Outcomes

TOPIC AREA	Original variable	Summary Health Risk Variable	Dichotomized Individualized Health Risk Variable (Risk vs. no risk)
EATING			
Sweetened beverage consumption	0, 1, 2, 3+	# of sweetened beverages consumed in a typical day	2-3+ vs 0-1
Fruit and vegetable consumption	0-5+	# of fruits and vegetables consumed in a typical day	0-3 vs. 4+/day
ACTIVITIES			

Physical activity (60+ minutes)	0-7	# of days with >60 minutes of physical activity in an average week	0-3 days/week vs. 4-7 days/week
Sleep	0-12+	# of hours of sleep on a typical night	0-7 hours vs. 8+ hours
SAFETY			
Seatbelt Use	4 pt. scale	Frequency of seatbelt use in a car	Not always vs. always
Helmet Use	4 pt. scale	Frequency of helmet use when bicycling	Not always vs. always
DUI/Riding with a DUI driver	Dichotomous	Yes vs. no	Yes vs. no
Texting while driving	4 pt. scale	Frequency of texting while driving (4-point scale)	NOT INCLUDED IN SUMMARY RISK VARIABLE
ALCOHOL AND DRUGS			
Drinking frequency	0-30	Decrease in # of days on continuous scale	≥1 (Ages 13-15) vs. 0 ≥2 (Ages 16-17) vs. 0-1 ≥3 (Age 18) vs. 0-2
Drinking quantity (typical or maximum)	0-15+	# of alcoholic drinks typically consumed per occasion	≥3 (Girls 13-17 and Boys 13) vs. 1-2 ≥4 (Girls 18 and Boys 14-15) vs. 0-3 ≥5 (Boys 16-18) vs. 0-4
Marijuana use frequency	0-30 days and/or 0-365 days	#of days used marijuana in the past 30 days and or year	≥1 days/month (Ages 13-15) vs. 0 ≥2 days/month (Ages 16-18) vs. 1 ≥1 days/year(Ages 13-15) vs. 0 ≥6 days/year (Ages 16-18) vs. 0-5
SEXUAL ACTIVITY			

Condom Use	4 point scale	Frequency of condom use with sexual intercourse	Not always vs. always (or not sexually active)
Birth control use	Dichotomous	Use of any birth control at last sexual intercourse (yes/no)	Not always vs. always (or not sexually active)
EMOTIONS			
Depression (PHQ-9)	0-27	Score on PHQ-9	Total score on PHQ 10 or higher vs. 0-9

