For *Aim 2*, analyses will be based on patient survey responses to the 8-item satisfaction scale, patient perception of PCP communication, and the summary health risk variable, which will all be treated as continuous response variables. The summary health risk variable constructed from a count of dichotomized key risk behaviors (as shown in Table 2). First, satisfaction levels and risk behaviors will be summarized for each period (pre- and post-intervention) and will be compared using two sample t-tests. For the main analysis, we will apply mixed effects models similar to those proposed in Aim 1 to examine the intervention effect. For patient satisfaction, PCP satisfaction, adolescent's perception of PCP communication and health risk behaviors, the analysis will be cross-sectional comparisons at one day following the primary care visit. Let Y_{ij} denotes the satisfaction at one-day post visit of adolescent j within PCP i , let X_{ij} denote whether the PCP has received intervention at the time of visit, then the following mixed effects model can be applied

$$Y_{ij} = \mu + \alpha X_{ij} + b_i + \varphi \text{Covariates} + \varepsilon_{ij},$$

where b_i accounts for within-PCP correlations for adolescents seen by the same PCP. The fixed effect α captures the intervention effect on the patient satisfaction. Similar model can be applied to PCP outcomes and we can account for within-clinic correlations as well.

When examining the intervention effects on adolescents individual risky behaviors (alcohol use, marijuana use, unprotected sexual activity, depression, physical activity, healthy food consumption, seatbelt and helmet use) at baseline, 3, 6, and 12 months after the primary care visit, same modeling framework as outlined for Aim 1 can be applied.

3.3.3 Heterogeneity of Treatment Effects.

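### Aim 2 sends health risk behaviours to a one-day comparison that has no scheduled data, and does not state the time points or the effect coefficient for the summary health risk variable

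*Combined protocol and SAP*

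**What the plan says.** Section 3.3.2 (Aim 2) names three responses: satisfaction, perception of PCP communication, and "the summary health risk variable, which will all be treated as continuous response variables". The summary variable counts the Table 2 behaviours scored as risk or no risk. For the main analysis the section promises "mixed effects models similar to those proposed in Aim 1". The next sentence then fixes the timing. It opens with "For patient satisfaction, PCP satisfaction" and continues: "perception of PCP communication and health risk behaviors, the analysis will be cross-sectional comparisons at one day following the primary care visit". The model displayed there has no time term, and its X is said to "denote whether the PCP has received intervention at the time of visit".

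A later paragraph, beginning "When examining the intervention effects on adolescents individual risky behaviors", applies the Aim 1 framework at baseline, 3, 6 and 12 months. It lists the behaviours one by one and does not mention the summary variable.

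The Aim 1 model has an intervention term α, time terms β_k and time-by-intervention terms γ_k. The plan gives a treatment-effect meaning to both α (mean responses) and γ_k (across time), and tests every coefficient with a Wald test. For an adolescent enrolled after the PCP's implementation, X is 1 at all assessments. Section 3.3.3 gives a version without the interaction, says similar models apply to adolescent outcomes, and calls α the treatment effect.

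**The concern.** The one-day rule for health risk behaviours points to a survey that does not collect them. The analyst must therefore replace it, and the replacement involves three choices that the text leaves open:

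- which time points the summary health risk variable uses;
- which coefficient or contrast is the Aim 2 result;
- how X is coded for a control-period adolescent whose PCP crosses over during follow-up.

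These choices can give different answers from the same data. If they are made after the data are seen, the Aim 2 behavioural result is not pre-specified.

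**Working it through.** **1. Schedule against analysis rule.**

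| Source | Time of health risk behaviours |
|---|---|
| Section 1.1, Aim 2 | baseline, 3, 6, 12 months |
| Section 3.1, T2 survey | motivation, PCP communication, experiences, satisfaction; no risk items |
| Table 1, six rows (alcohol/marijuana, fruit and vegetables, physical activity, sexual risk, PHQ-9, safety) | T1, T3, T4, T5 in 6 of 6; T2 in 0 of 6 |
| Section 3.3.2, one-day sentence | T2 |
| Section 3.3.2, longitudinal paragraph | baseline, 3, 6, 12 months; individual behaviours only |

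The one-day sentence is the only entry that places these behaviours at T2.

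**2. The summary variable.** The Table 1 note attached to the health risk rows says "See Table 2 for Individual Health Risk Outcomes and Summary Risk Variable", which suggests that the summary variable follows the same schedule. Section 3.3.2 also gives health risk behaviours as its example of repeated assessment. Both imply the longitudinal model; neither states it for this variable.

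**3. What α estimates.** For post-implementation adolescents T1 comes before the feedback (section 3.1) and the visit, yet X = 1 there. Assume T1 is the reference time, X is constant within adolescent, data are complete, and the effect is 0 at T1 and d at T3, T4 and T5.

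- With interaction: α = difference at T1 = 0; γ_k = d − 0 = d; average post-visit contrast = α + mean(γ_k) = d.
- Without interaction: α = (0 + d + d + d)/4 = 0.75d.

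For an assumed d = −0.40 SD this gives α = 0, γ_k = −0.40 and average contrast −0.40 in the first form, and α = −0.30 in the second. A simulation agreed: α −0.002; γ_k −0.398, −0.402, −0.399; average −0.402; no-interaction α −0.302. It used 1000 runs, 30 PCPs with 5 control-period and 5 post-implementation adolescents each, and assumed variances of 0.05 (PCP), 0.45 (adolescent) and 0.50 (residual).

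**4. Coding of X after crossover.** Let p_k be the proportion of control-period adolescents whose PCP has crossed over by time k, and c the effect of that crossover on adolescents already seen. With X fixed at the index visit, the contrast at time k is d − p_k·c. This equals d if c = 0, and d(1 − p_k) if c = d.

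The p_k depend on the spacing of the steps. The timeline figure is not available in the text reviewed, so the three patterns below (T3/T4/T5) are assumptions. Their means are (10+20+40)/3 = 23.3%, (25+50+75)/3 = 50% and (50+75+90)/3 = 71.7%. The table gives the average T3 to T5 contrast for d = −0.40. Index-visit values come from the formula, for example −0.40 × (1 − 0.233) = −0.307. Switching-X values come from the simulation set-up in step 3.

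| Crossover effect c | Coding of X | 10/20/40% | 25/50/75% | 50/75/90% |
|---|---|---|---|---|
| 0 | index visit | −0.400 | −0.400 | −0.400 |
| 0 | switching | −0.228 | −0.148 | −0.117 |
| −0.20 | index visit | −0.353 | −0.300 | −0.257 |
| −0.20 | switching | −0.315 | −0.273 | −0.258 |
| −0.40 | index visit | −0.307 | −0.200 | −0.113 |
| −0.40 | switching | −0.403 | −0.399 | −0.399 |

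The time-specific terms are affected too: with index-visit coding, full crossover effect and 90% switched, γ at T5 is −0.40 × (1 − 0.90) = −0.04. Each coding recovers d only under its own assumption about c.

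**The case against.** The intended analysis can largely be recovered. Section 1.1, Table 1 with its note, and the general sentence on Aim 1-type models all point to a longitudinal analysis, and section 3.3.2 says other adolescent-reported outcomes can be modelled like motivation. An analysis plan is also to be presented to the study team and advisory board before the analyses. This stands as evidence of intent, and that later plan is a natural place for the correction. It does not make the one-day sentence executable. Adding the items to T2 would not help much either: the substance-use items look back 30 days, so a one-day report would describe almost entirely pre-visit behaviour.

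A reader might infer that the summary variable is explicitly tied to the impossible time point alone. The text does not go that far: the one-day sentence says health risk behaviours without naming the summary variable, and its displayed model defines Y as satisfaction.

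A reader might also infer that the treatment effect is lost. It is not, because the γ_k are in the Aim 1 model, are given a treatment-effect meaning and are tested. What is missing is a statement of which coefficient or contrast is the result.

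Finally, a reader might infer that X should plainly be fixed at the index visit. Section 3.1 (groups by appointment period) and the one-day model support that reading. But the Aim 1 framework asks for an indicator by PCP and time point, allows differing numbers of post-intervention assessments and uses within-adolescent information, all of which point to a time-varying X. The table above does not favour either coding.

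**Conclusion.** The contradiction is certain from the text: 0 of 6 health risk rows are scheduled at the time point to which section 3.3.2 assigns them. It is an error in the analysis text, not a gap in data collection. The summary health risk variable lacks an explicit usable time point, although the intended one can be inferred.

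The point about α is conditional. With T1 as reference and no effect before the visit, α in the interaction model is a pre-visit difference, and α in the no-interaction model is 75% of the follow-up effect. The plan does not state the reference time.

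The coding of X is an unresolved choice of estimand. Index-visit coding gives the full effect only if crossover leaves adolescents already seen unaffected; switching X gives it only if crossover affects them fully. The figures for this part rest on assumed switching proportions and variances, and show only that the choice can matter.

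This should be fixed before analysis.

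**What to change.** - Remove health risk behaviours from the one-day sentence.
- Name the summary health risk variable in the longitudinal paragraph, with T3, T4 and T5 as outcome times and T1 as a pre-visit baseline.
- State that the effect is read from the post-visit contrasts, time-specific or averaged, and say which. It should not be read from α at T1 or from a no-interaction α that pools T1.
- Reconcile the definition of X for control-period adolescents whose PCP crosses over during follow-up: section 3.1 and the one-day model use status at the appointment, while the Aim 1 framework uses PCP and time point. State the estimand that follows and its assumption about crossover; the other coding can serve as a sensitivity analysis.
- Minor: name caregiver satisfaction, an Aim 2 objective collected at T2, in the one-day model. Clarify or remove PCP satisfaction, since section 3.1 says PCPs complete no study questionnaires.

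All the data needed are already scheduled. Apart from X these are wording changes; the coding of X needs a decision by the study team.

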2.1. Sample Size

We plan to enroll approximately 300 adolescent (age 13-18) and parent dyads who have an appointment with a participating provider affiliated with one of six participating practices in the Puget Sound Pediatric Research Network (PSPRN). We also plan to enroll approximately 30 PSPRN providers (about 5 providers per clinic).

2. Gender of Subjects

This study does not have any gender-based restrictions. However, given that women are more frequently primary caregivers and PCPs, we estimate the following gender distribution in our study population:

Adolescents: 150 Females and 150 Males

Caregivers: 240 Females and 60 Males

PCPs: 18 Females and 12 Males

3. Age of Subjects

Participants will include adult *caregivers and PCPs* (over the age of 18 years) and *adolescents* (age 13-18). As health risk behaviors typically begin in adolescence and persist into adulthood, we are targeting adolescents rather than children less than 13 years of age.

4. Racial and Ethnic Distribution

The proposed study population will include a wide cross section of adolescent patients and their caregivers, including many families of ethnoracial minority status. We will monitor diversity in our sample throughout the course of recruitment and adapt recruitment efforts as needed to assure a representative sample. The Central Puget Sound geographic area, where our study population is situated, consists of the following approximate ethnic and racial breakdown:

- 73% White
- 5% African American
- 12% Asian, Hawaiian or Other Pacific Islander
- 1% American Indian or Alaska Native
- 9% some other race (alone) or two or more races

In addition, 9% of individuals in this geographic area are of Hispanic or Latino ethnic background.

5. Inclusion Criteria

Eligible caregivers will have a child 13 to 18 years old who has an appointment with a participating provider at a PSPRN clinic and will be able to understand English.

Eligible adolescents will be 13 to 18 years old, have an appointment with a participating provider at a PSPRN clinic and will be able to understand English.

Eligible PCPs will include providers (i.e., pediatricians, family practitioners, physician assistants and nurse practitioners) affiliated with a PSPRN clinic who are following a panel of adolescent patients and will be able to understand English.

6. Exclusion Criteria

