3.1. Study Design

This study will evaluate the effect of I-ACT with Check Yourself on adolescent-perceived quality of care (i.e., satisfaction and perception of PCP communication), motivation for health, and health risk behaviors using a stepped wedge study design. The study will take place in 6 participating PSPRN affiliated clinics, where the system of interventions (I-ACT with Check Yourself) will be rolled-out sequentially to the clinics, chosen in random order, over spaced time intervals (see Figure 1). We refer to pre-implementation of I-ACT with Check Yourself, as the control period and post-implementation as the intervention (i.e., case) period.

Figure 1: Stepped Wedge Study Design and Timeline

We anticipate that approximately 30% of youth approached will participate in the study. Thus, we will invite approximately 1000 adolescent/caregiver dyads to participate in the study, in order to yield 300 adolescent/caregiver dyad participants in our total sample. Upon enrollment, caregiver participants will be asked to complete a brief (10-minute) web-based questionnaire about their education/occupation, their adolescent's health history, and an open-ended question about what they would like to get from PCPs for themselves and their adolescent. Adolescents who enroll in the study will receive either electronic health screening alone (i.e., control group) if

their clinic appointment occurs in the pre-I-ACT implementation period or Check Yourself (i.e., intervention group) if their clinic appointment occurs in the post-implementation period.

At baseline (T1), adolescents will be asked to complete a web-based screening survey that includes questions about guideline-recommended health risk behavior screening areas, including substance use, nutrition, physical activity, sexual behavior, depressive symptoms, and safety. The screener questions themselves are current standard of care. Adolescents will also be asked to report their age, gender, race/ethnicity, interest in discussing health risks with the PCP, and self-efficacy.

Adolescents in the control group will complete the web-based screening survey for research purposes, but neither they nor their PCP will receive feedback about their health behaviors. PCPs will screen and counsel the patient as they would normally do under usual care conditions, consistent with the current standard of care.

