3.3. Data Analysis and Data Monitoring

3.3.1 *Strategies to Minimize Missing Data.*

At the time of enrollment, we will gather the preferred and all available email addresses, phone numbers (including mobile for text messaging), and social networking inbox addresses for eligible adolescents. To confirm accuracy of the email address, participant payments will be sent electronically, via email, and participants will be instructed to contact study staff if payment is not received. We will also collect phone numbers for 3 friends or family members who would know how to reach the participant if we do not. Our experience is that we can maintain >85% of our enrollees over the course of the study. Despite our best efforts, we expect some attrition over the course of follow up, which has been factored into our sample size calculations. In the case that an adolescent does not have an email address, surveys will be completed by phone and payments will be sent via mail.

Maintaining statistical power is a key consideration. We will implement various recommended strategies for maximizing power within the current design, including use of covariates in data analyses when appropriate, preventing attrition and missing data, implementing advanced missing data analyses such as multiple imputation techniques using reliable measures, and maintaining integrity of the intervention throughout the study. For all analyses, we will start with models using all available data, not just complete cases. In addition we will apply inverse probability weighted methods to adjust for missing data and conduct sensitivity analyses looking at how other estimates are impacted by including the variables with missing values.

3.3.2 *Data Analysis.*

Data from the web-based surveys will be uploaded into STATA analytic software. Prior to analysis, all variables will be checked for validity, missingness, and distributional assumptions. Preliminary analyses required for variable construction, any required imputation of missing data, assessment of psychometric properties of scale scores, and assessment of the validity of study variables will be completed before analyses assessing

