in which Y_{ijk} denotes the health motivation reported by j th patient within i th provider at k th time interval, X_{ijk} is a binary indicator of exposure to the intervention for the provider and the predictor of interest, T_k is a binary indicator of the k th assessment, b_i and b_{ij} are PCP and adolescent specific random effects that account for the within PCP and within adolescent correlations, and ε_{ijk} is the error term. Additional patient-level or PCP-level confounding variables can be adjusted in the model as well.

With this model, the fixed effects α captures the treatment effects on mean responses and time-by-intervention interaction coefficients γ_k 's captures the treatment effects across time. Fixed effects β_k 's aim to capture any temporal trend or learning effects. Using this approach, both within-adolescents and between adolescents information will be used to estimate the treatment effects. All coefficients will be tested using Wald test. Also note this

model framework is flexible enough that a patient can be enrolled at any time during the study and the model can accommodate different numbers of post-intervention assessments. For example, for an adolescent enrolled after his/her PCP has received intervention, all X_{ijk} 's would take value 1 for that subject.

We will apply linear mixed effects models for Gaussian outcome Y_{ijk} , and generalized linear mixed effects models for other types of outcomes (e.g., logistic model for binary outcome).

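### Neither printed model for the health risk behaviours conditions on the adolescent's own T1 value, and the plan does not say which coefficient is the treatment effect

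*Combined protocol and SAP*

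**What the plan says.** Section 3.2, Table 1, gives the time points of the health risk dimensions as "T1(A), T3(A), T4(A), T5(A", so they are asked at baseline, 3, 6 and 12 months but not at one day (T2). Section 3.1 places T1 before the appointment, and intervention adolescents get their feedback only after finishing the T1 survey.

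Section 3.3.2, Aim 2, lists among its outcomes "the summary health risk variable, which will all be treated as continuous response variables". It then says that for "health risk behaviors, the analysis will be cross-sectional comparisons" at one day after the visit. The model printed there has exposure X_ij, a PCP random effect, an unspecified covariate term and error.

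The individual behaviours, at baseline and the three later surveys, are sent to the Aim 1 framework. That model has α for exposure, β_k for assessment, γ_k for exposure by assessment, and PCP and adolescent random effects. The γ_k are described as the part that "captures the treatment effects across time". For an adolescent enrolled after the PCP's training, X is 1 on every row, the T1 row included. The reference assessment is not stated, and both α and γ_k are described as treatment effects.

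Sections 3.3.1 and 3.3.2 allow covariates in general terms. Neither names the T1 value of the outcome.

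**The concern.** A baseline value of the same outcome is usually the strongest single predictor of follow-up, and here it is already collected. If the model does not condition on it, stable differences between adolescents in habitual risk stay in the error term. Section 3.3.1 treats power as a key consideration and lists covariates as a means to it, so leaving this one unnamed works against the plan's own aim.

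Two further gaps sit in the same place. The summary-score comparison is set at a survey that does not collect its components, so it cannot be run as written. In the longitudinal model, α, γ_k and α + γ_k answer different questions with different precision, and the choice among them is left until the data are in hand.

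**Working it through.** **Inputs from the documents.** Section 2.1: "We plan to enroll approximately 300 adolescent (age 13-18) and parent dyads" and "approximately 30 PSPRN providers (about 5 providers per clinic". Section 3.1: about 1000 dyads invited, with "approximately 30% of youth approached will participate in the study". Section 3.3.1: "we can maintain >85% of our enrollees over the course of the study".

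**The plan's own figures.** 1000 × 0.30 = 300 adolescents; 6 × 5 = 30 PCPs; 300 / 30 = 10 adolescents per PCP. The sample size itself cannot be reproduced, because effect size, SD, ICC, alpha and power are not given. Neither is the T1-to-follow-up correlation ρ. Everything below that uses ρ or an ICC is an assumption.

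**What the longitudinal coefficients mean.** Take T1 as reference. The exposed-minus-unexposed difference is α at T1 and α + γ_k at follow-up k. So γ_k = (α + γ_k) − α is a difference in change from T1, and α + γ_k is a follow-up difference. If the true effect is 0 at T1 and 1 afterwards, the model returns α = 0 and γ_k = 1. Both contrasts are then on target and differ only in precision.

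**Variances for one follow-up, continuous outcome, in units of SD².**

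- Follow-up only: 1
- Adjusted for T1: 1 − ρ²
- Change from T1: 2(1 − ρ)

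The precision lost relative to adjustment is 1 − (1 − ρ²)/1 = ρ² for follow-up only, and 1 − (1 − ρ²)/[2(1 − ρ)] = (1 − ρ)/2 for change.

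| ρ | Follow-up only loses | Change loses | Adjusted adolescents matching 300 unadjusted, 300(1 − ρ²) |
|---|---|---|---|
| 0.2 | 4% | 40% | 288 |
| 0.3 | 9% | 35% | 273 |
| 0.5 | 25% | 25% | 225 |
| 0.7 | 49% | 15% | 153 |

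**The same in the printed Aim 1 model.** Generalised least squares with 30 PCPs × 10 adolescents, half exposed within each PCP, rows at T1, T3, T4 and T5, equal correlation between assessments, PCP ICC 0.02 and no attrition. The comparator is the same model with the exposure effect at T1 fixed at zero.

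| ρ | SE, α + γ_k | SE, γ_k | SE, T1 effect fixed at 0 | α + γ_k loses | γ_k loses |
|---|---|---|---|---|---|
| 0.2 | 0.1143 | 0.1461 | 0.1124 | 3% | 41% |
| 0.3 | 0.1143 | 0.1366 | 0.1095 | 8% | 36% |
| 0.5 | 0.1143 | 0.1155 | 0.0997 | 24% | 26% |
| 0.7 | 0.1143 | 0.0894 | 0.0823 | 48% | 15% |

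For example, at ρ = 0.5: 1 − (0.0997/0.1155)² = 0.255. The SE of α + γ_k does not move with ρ: with a free exposure effect at every assessment, the adolescent random effect brings in nothing from T1. With ICC 0.05, α + γ_k loses 2.5% to 47% and γ_k 42% to 16% over the same range of ρ.

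**Effect on power, as an illustration.** Assume a follow-up comparison of the summary score with 255 analysed (300 × 0.85), 6 clinics, 30 PCPs, 7 calendar periods with period terms, and ICCs of 0.01 (clinic) and 0.02 (PCP). Multiply only the individual-level residual by 1 − ρ². The SE of α is 0.181 SD unadjusted, and 0.174, 0.160 and 0.135 at ρ = 0.3, 0.5 and 0.7. Power for an assumed 0.40 SD effect at two-sided 5% goes from 60% to 64%, 71% and 84%.

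**The case against.** The case against is substantial, and much of it stands.

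- **Baseline is not ignored throughout.** A reader might infer that no risk-behaviour effect takes account of baseline. The documents do not support that: γ_k with T1 as reference is a change contrast and removes T1 imbalance. What remains there is an inefficient choice, and an unnamed one.
- **Adjustment is not excluded.** Both models have an open covariate term, and a cross-sectional outcome model may contain a baseline covariate. Section 3.3.2 also has an analysis plan presented to the team and advisory board before each question is analysed. This stands: the fault is that T1 is not prespecified, not that it is barred.
- **One figure for the loss.** It is tempting to say that a quarter of the precision is lost. That is ρ² at ρ = 0.5, a value the documents do not give, and the two losses move in opposite directions with ρ. Section 3.3.2 expects weak within-patient correlation, but its reason is that different patients are surveyed at each time point. That does not describe the same adolescents at T1, T3, T4 and T5, so it does not settle ρ.
- **Adjustment is not always better.** Its clear advantage needs equal expected T1 values in the two periods. Adolescents are not individually randomised and enrol in different periods. If the periods differ stably at T1, a change contrast can be unbiased while adjustment leaves some bias. Chance imbalance, by contrast, is already in the standard error and is not a second harm.
- **Binary outcomes.** Table 2 dichotomises the individual behaviours, and binary outcomes get logistic models. The formulas above do not carry over, and adding T1 changes the conditional odds ratio being estimated.

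**Conclusion.** The point holds as a gap in specification with a cheap remedy. Neither printed model conditions on the adolescent's own T1 value, the summary-score comparison is placed at a survey without the data, and the longitudinal treatment effect is not identified among α, γ_k and their sum.

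For continuous outcomes, over assumed ρ of 0.2 to 0.7, a follow-up-only contrast gives up about 4% to 49% of precision and γ_k about 41% to 15%. A weak correlation makes the first loss small and the second large, so no value in that range makes both negligible. For the summary score alone the gain is modest at ρ = 0.3 (60% to 64% power in the illustration) and material from about 0.5. These sizes rest on assumed ρ and ICCs, equal expected T1 values between periods, and continuous outcomes.

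**What to change.** In section 3.3.2, Aim 2:

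1. Set the summary health risk comparison at T3, T4 and T5, where its components are measured, and add the T1 summary score: Y_ijk = μ + αX_ij + λY_ij,T1 + the plan's time terms and random effects + error.
2. For motivation and the individual behaviours, either take T1 out of the outcome rows and enter it as a covariate, or keep the T1 rows and fix the exposure effect at T1 at zero.
3. State the reference assessment and name the coefficient, or combination of coefficients, that is the treatment effect.
4. Handle missing T1 values with the multiple imputation already planned in section 3.3.1.
5. Keep the unadjusted and change-from-T1 results as sensitivity analyses. A difference between periods in T1 reporting enters the effect with weight of about ρ under adjustment, 1 under change and 0 unadjusted, so agreement among the three is informative.
6. For binary outcomes, say that the odds ratio is conditional on T1.

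The cost is wording and one model term, with no new data and no change to enrolment or surveys.
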